## **9.8 Analysis of Secondary Objectives**

The proportion of patients who had cancer detected by both the standard of care imaging (MRI) and the Ga-PSMA-11 PET imaging will be calculated, along with exact 95% confidence intervals. A similar approach will be used for other secondary outcomes in Section 9.4.2 to compare the cancer detection of the mpMRI and Ga-PSMA-11 detection method to the surgical observations and the clinical tissue histopathology findings.

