### **4.2 Secondary**

Evaluate how knowledge of the PSMA-PET can inform treatment planning.

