### 9.3 Sample Size

Table 1: Sample size calculation:

	sensitivity= 0.80	sensitivity= 0.85	sensitivity= 0.90	sensitivity= 0.95
Error allowed (d)= 7.5%	46	37	27	14
Error allowed (d)= 10%	27	21	15	8

Our sample size is based on the key primary endpoint of sensitivity to detect clinically significant (Gleason >6 and >5mm) cancer overall. In the Table above we summarized the sample size required to achieve a certain degree of accuracy for different sensitivity levels. All the calculations are based on the normal approximation of the binomial distribution. For this pilot, we will also assume the samples within each patient are independent statistically. Each patient has six samples for diagnostic testing (sextants) and the prevalence of cancer per sextant is estimated to be 40% (Eiber et al., 2016). The rows (d) present the marginal maximal error under 95% confidence interval and the columns represent the sensitivity rate. The numbers in Table 1 represent the required number of patients needed for each different combination of marginal error (d) and sensitivity rate. In other words, for a sensitivity of 90% and a marginal error of 7.5%, we

are 95% sure that the sensitivity lies between 82.5% and 97.5% if we enroll 27 patients. Based on Table 1, the maximal sample size is 46 assuming the sensitivity is 80%. Therefore, we decided 36 patients was adequate to ensure that the proposed trial can achieve certain accuracy of the sensitivity across the majority the scenarios considered in Table 1.

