### 9.4.2 Secondary

- Lesion based analysis of accuracy
- For 3+4: Sensitivity and specificity of mpMRI based on Gleason %pattern 4
- For 3+4: Sensitivity and specificity of PET-CT based on Gleason %pattern 4
- Sensitivity and specificity for extra-capsular extension (mpMRI vs PET-CT)
- Sensitivity and specificity for seminal vesicle invasion (mpMRI vs PET-CT)
- Impact of PSMA PET-CT on treatment plan for surgery:
  - Additional lesions found, Additional sextants involved, extra-capsular extension detected, seminal vesicle invasion detected, lymph node invasion detected.
- Impact of PSMA PET-CT on treatment plan for biopsy:
  - Additional lesions found, Additional sextants involved

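### Section 9.8's one explicit statistic, detection by both MRI and PET, cannot show what PET adds, and the section assigns no paired or patient-clustered analysis to the secondary outcomes.

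*Combined protocol and SAP*

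**What the plan says.** The secondary objective in section 4.2 is: "Evaluate how knowledge of the PSMA-PET can inform treatment planning".

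Section 9.8 gives the analysis in two sentences. The first defines one statistic, "The proportion of patients who had cancer detected by both the standard of care imaging (MRI) and the" PSMA PET scan, to be reported "along with exact 95% confidence intervals". The second extends it: "A similar approach will be used for other secondary outcomes in Section 9.4.2", with detection by the two methods compared with surgical and histopathology findings.

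The outcomes so covered include "Lesion based analysis of accuracy" and, as measures of impact on the surgery and biopsy plans, "Additional lesions found, Additional sextants involved". They also include extra-capsular, seminal vesicle and lymph node findings.

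Section 9.8 does not state the unit of analysis for these outcomes, a paired comparison of PET with MRI, or any adjustment for several observations in the same man. Section 9.7 has two of these tools, GEE and a McNemar test, for the primary sextant analysis only.

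**The concern.** What PET contributes to planning lies in the discordant findings. Those seen on PET but not MRI and confirmed by pathology are the gain. Those seen on PET alone and not confirmed are the cost. Findings seen on MRI alone show what PET would miss. The statistic that 9.8 spells out is the concordant cell, which is silent on all three.

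The second issue is the interval. An exact binomial interval treats each unit as independent. That is right for one yes/no result per man. It is not right for lesions or sextants, several of which come from the same man, and the background section says that the disease is multifocal in more than 80%. If the exact method is carried to that level, the reported precision of the lesion and sextant results could be overstated. Section 4.3 makes pilot data for larger trials the exploratory aim, so both the discordant counts and fair intervals would be wanted by whoever designs the next study.

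**Working it through.** **The plan's own figures.** Section 9.8 states no number to reproduce. The nearest is the sample size table in 9.3, which fixes the units per man: 6 sextants × 0.40 prevalence = 2.4 positive sextants. With n = 1.96² × p(1 − p) / d² / 2.4, rounded up, I get 46/37/26/14 at d = 7.5% and 26/21/15/8 at d = 10%. The plan has 46/37/27/14 and 27/21/15/8. Six of the eight cells match and two differ by one patient. That table assumes independence within a man, but it says so for sample size only.

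**Step 1: does the both-positive proportion carry information on added yield?** Section 9.3 sets the size: "we decided 36 patients was adequate". The cell counts below are illustrative, since the documents give none.

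- With 27 of 36 positive on both, the estimate is 75% and the exact interval 57.8% to 87.9%. The other 36 − 27 = 9 men can fall anywhere, so PET-only can be 0 to 9 men (0% to 25%).
- With 18 of 36 positive on both, the estimate is always 50.0% (32.9% to 67.1%):

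| PET only | MRI only | Neither | PET minus MRI | Exact McNemar p |
|---|---|---|---|---|
| 10 | 2 | 6 | (10 − 2)/36 = +22.2 points | 0.039 |
| 6 | 6 | 6 | 0 | 1.0 |
| 2 | 10 | 6 | (2 − 10)/36 = −22.2 points | 0.039 |

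The same reported result fits PET being better, equal or worse. This step needs no assumption about correlation.

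**Step 2: what if exact intervals are used per lesion or per sextant?** The number of lesions per man and the within-man correlation ρ are not in the documents, so both are assumptions. The design effect is 1 + (m − 1)ρ, and an interval that assumes independence has width 1/√(design effect) relative to one that allows for clustering. Coverage comes from simulating 36 men with beta-binomial clustering, true proportion 0.5 to 0.9, and a nominal 95% exact interval.

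| Units per man (m) | ρ | Design effect | Relative width | Coverage |
|---|---|---|---|---|
| 2 | 0.1 | 1.1 | 0.95 | about 95-96% |
| 2 | 0.2 | 1.2 | 0.91 | about 93-95% |
| 3 | 0.4 | 1.8 | 0.75 | about 87-89% |
| 6 | 0.3 | 2.5 | 0.63 | about 79-83% |

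With the plan's own 2.4 positive sextants per man and a true proportion of 0.8 to 0.9, coverage is about 95% at ρ = 0.1, 92-93% at 0.2 and 90-91% at 0.3.

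The width ratio alone overstates the problem at low correlation. Exact intervals are conservative: with independent units in these settings they cover about 96-97%, and that margin absorbs a little clustering.

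**The case against.** The best defence is that 9.8 should be read with the endpoints that it points to. The added lesions and sextants in 9.4.2 are naturally read as PET findings beyond standard imaging, 9.8 sets detection against surgery and histopathology, and sections 7.3.3 and 7.3.4 track what PET contributed to decisions. A reader might infer from the both-positive statistic that the secondary objective goes unanswered. The documents do not support that, because these endpoints address it in part. What they leave open is the MRI-only count, a separate count of unconfirmed PET-only findings, and how any of this is to be compared.

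Section 9.7 also has a McNemar test, which rests on the discordant cells, so the plan as a whole does not lack paired analysis. This stands, but the test is assigned to sensitivity and specificity in the primary analysis and not to the outcomes in 9.4.2.

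A reader might also infer that 9.8 treats lesions as independent and that its intervals are therefore too narrow. The text does not go that far. Similar does not mean identical, no unit is stated, and extra-capsular, seminal vesicle and nodal findings can be counted once per man, as can any added lesion as yes or no. For such outcomes the exact interval is correct. The loss of coverage arises only if the method is used per lesion or per sextant, and its size depends on assumed inputs.

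Finally, detection by both may have been meant as detection by each. The text does not say so, and two separate proportions would still lose the pairing. That this is a small, hypothesis-generating pilot is fair, and it limits the consequence to interpretation.

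**Conclusion.** The point holds in a limited form. The only statistic that 9.8 makes explicit cannot show PET's added yield, whatever the correlation or case mix, and the section assigns no paired analysis to the secondary outcomes. The objective is partly served by the 9.4.2 endpoints, so this is a gap in the stated analysis and not a failure to collect the right data.

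The interval problem is conditional. It applies if the exact method is used per lesion or per sextant. It is negligible at 2 lesions per man and correlation 0.1, small at 0.2 (about 93-95% coverage), and material at 3 lesions and 0.4 (about 87-89%) or with all six sextants at 0.3 (about 79-83%). These correlations and lesion counts are assumptions. Outcomes counted once per man are unaffected. No confirmatory conclusion rests on these results, so this is a change that should be made before analysis, not a fault that undermines the trial.

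**What to change.** Amend section 9.8 as follows.

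1. Replace the both-positive proportion with the paired PET-by-MRI table against pathology: both, PET only, MRI only, neither. Report PET-only confirmed and PET-only unconfirmed findings separately.
2. State the unit of analysis (man, sextant or lesion) for each outcome in 9.4.2.
3. Keep exact 95% intervals for outcomes counted once per man.
4. Use patient-clustered intervals, by GEE as already planned in 9.7 or by a bootstrap that resamples men, for outcomes analysed per lesion or per sextant.

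The cost is revised wording and slightly more analysis, and some lesion and sextant intervals will be wider. No extra patients or procedures are needed.

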# **10 DATA FORMS AND SUBMISSION SCHEDULE**

This study will utilize the secure, web-based, Research Electronic Data Capture (REDCap) system for data input. REDCap was developed by Vanderbilt University and is provided by Indiana University through their community license. REDCap is managed by the Indiana University Department of Biostatistics and secured by University Information Technology Services Advanced IT Core. Access to the password protected database will be limited to the investigators of this study, and any data that is distributed will be either de-identified or authorized by written permission from the subject.

All source documents are to remain in the patient's clinic file. All documents should be kept according to applicable federal guidelines.

# **11 DATA AND SAFETY MONITORING PLAN**

This study will be conducted in accordance with the IU Simon Cancer Center Institutional DSMP for High Risk Trials.

Investigators will conduct continuous review of data and subject safety. Weekly review meetings for high risk trials are required and will include the principal investigator, clinical research specialist and/or research nurse (other members per principal investigator's discretion). Weekly meeting summaries should include review of data and subject safety by including for each dose level: the number of subjects, significant toxicities as described in the protocol, dose adjustments and responses observed. Study teams should maintain meeting minutes and attendance for submission to the DSMC upon request.

### **Data and Safety Monitoring Committee**

The IUSCC Data and Safety Monitoring Committee (DSMC) is responsible for oversight of subject safety, regulatory compliance, and data integrity for this trial. The DSMC will review this study semi-annually to review overall trial progress, toxicity, compliance, data integrity, and accrual per the Institutional DSMP.

Furthermore, the DSMC conducts an administrative review of serious adverse events (SAEs), deviations, reportable events, and any other outstanding business. Major issues may require further DSMC review or action.

For any increase in frequency of grade 3 or above adverse events (above the rate reported in the Investigator Brochure or package insert), the principal investigator will notify the DSMC Chair immediately. The notification will include the incidence of study adverse events, grades, and attributions, as well as investigator statements regarding comparison with risks per the IB/ package insert.

At any time during the conduct of the trial, if it is the opinion of the investigators that the risks (or benefits) to the subject warrant early closure of the study, the DSMC Chair and Compliance Officer must be notified within 1 business day via email, and the IRB must be notified within 5 business days. Alternatively, the DSMC may initiate suspension or early closure of the study based on its review.

### **11.1 IND Annual Reports**

For trials with an IND held locally by the IU principal investigator or university, the IND Annual Report will be prepared and submitted to the Compliance Team. This report will be reviewed by the DSMC at the time of FDA submission.

## **11.2 Study Auditing and Monitoring**

All trials conducted at the IUSCC are subject to auditing/monitoring. Reports will be forwarded to the DSMC for review.

## **11.3 Data Management/OnCore Reporting Requirements**

The DSMC reviews data and study progress directly from Oncore; therefore, timely data entry and status updates are vital. Study data must be entered within Oncore promptly, no later than one week from study visit occurrence. Subject status in Oncore will be updated in real time, as this may affect overall trial enrollment status. Global SAEs and deviations will be reviewed on a monthly basis by the DSMC Chair directly from Oncore.

## **11.4 OnCore Safety Reporting**

In addition to protocol- and regulatory-required safety reporting, all serious adverse events (SAEs) will be captured in the Oncore system within 1 business day of notification. Initial SAE reporting will include as much detail as available, with follow-up to provide complete information.

Attributions will be assessed to study drugs, procedures, study disease, and other alternate etiology.

## **11.5 Study Accrual Oversight**

Accrual data will be entered into the IU Simon Cancer Center OnCore system. The Protocol Progress Committee (PPC) reviews study accrual twice per year while the PPC coordinator reviews accrual quarterly.

## **11.6 Protocol Deviation Reporting**

Protocol deviations will be entered into OnCore within 5 days of discovery and reviewed by the DSMC Chair on a monthly basis. Findings will be reported to the full DSMC at the time of study review. For serious or repetitive protocol deviations, additional action may be required by the DSMC.

## 12 ADVERSE EVENTS

### 12.1 Definitions of Adverse Events

#### 12.1.1 Adverse Event

An adverse event (AE) is defined as any untoward medical occurrence associated with the use of a drug in humans, whether or not considered drug related. An adverse event can be any unfavorable and unintended sign (e.g. an abnormal laboratory finding), symptom, or disease temporarily associated with the use of a drug, without any judgment about causality. Adverse events will be graded according to the NCI Common Toxicity Criteria, Version 4.0 (Appendix A).

#### 12.1.2 Serious Adverse Event (SAE)

A serious adverse event is any untoward medical occurrence resulting in one or more of the following:

- Results in death or ANY death occurring within 28 days of last dose of study drug (even if it is not felt to be drug related)
- Is life-threatening (defined as an event in which the patient was at risk of death at the time of the event; it does not refer to an event which hypothetically might have caused death if it were more severe)
- Requires inpatient hospitalization or prolongation of existing hospitalization

NOTE: Hospitalizations that are not considered SAEs are:

- Hospitalization planned prior to first administration of study drug
- Hospitalization for elective treatment of a pre-existing condition unrelated to the study medication
- Results in persistent or significant disability/incapacity
- Is a congenital anomaly or birth defect
- Is an important medical event (defined as a medical event(s) that may not be immediately life-threatening or result in death or hospitalization but, based upon appropriate medical and scientific judgment, may jeopardize the patient or may require intervention (e.g., medical, surgical) to prevent one of the other serious outcomes listed in the definition above). Examples of such events include, but are not limited to, intensive treatment in an emergency room or at home for allergic bronchospasm; blood dyscrasias or convulsions not resulting in hospitalization; or the development of drug dependency or drug abuse.

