## PROTOCOL SYNOPSIS

Primary Objectives:	Define the accuracy of $^{68}\text{Ga}$ -PSMA-11 PET-CT for detecting the location and size of clinically significant prostate cancer lesions in low and intermediate risk disease.
Secondary Objectives:	Evaluate how knowledge of the PSMA-PET might inform treatment planning.
Exploratory Objectives:	Generate pilot data to be validated in larger studies
Study Design:	Prospective, early phase clinical trial, single arm
Test Factor/Exposure:	Intravenous injection of $^{68}\text{Ga}$ -PSMA-11 and detection with PET-CT scanner
Duration of Treatment:	Patients will undergo injection of $^{68}\text{Ga}$ -PSMA-11 PET-CT and pre-treatment MRI scan and followed until biopsy and/or surgical resection.
Enrollment:	Subject accrual is planned for 24 months
Inclusion Criteria:	
 
1. <math>\geq 18</math> years of age
 
2. Must provide written informed consent
 
3. Presence of low or intermediate risk prostate cancer or at risk of having intermediate risk cancer 
 
a. Intermediate risk prostate cancer: 
 
i. Grade group 2 = 3 + 4, or
 
ii. Grade group 3 = 4 + 3
 
 
 
b. At Risk of intermediate risk prostate cancer: 
 
i. 4K score <math>\geq 20\%</math>, or
 
ii. Select MDx <math>\geq 20\%</math>, or
 
iii. PSA Density <math>\geq 0.15</math>
 
iv. Grade group 1 = 3+3
 
 
 
 
 
4. Scheduled for MRI or has recently completed SOC MRI (within 6 months) for further biopsy, surgical removal or focal therapy.
 
5. Willing and able to lie still for approximately 50 minutes in an enclosed space for the CT
 

[figure not shown]
Exclusion Criteria:	
 
1. Participation in another investigational trial involving research exposure to ionizing radiation concurrently or within 30 days.
 
2. Does not meet safety criteria for MRI scan (e.g. metal implant that is not allowed).
 
3. Significant acute or chronic medical, neurologic, or illness in the subject that, in the judgment of the Principal Investigator, could compromise subject safety, limit the ability to complete the study, and/or compromise the objectives of the study.
 

Number of Subjects:	36 patients

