### 7.3.2 Imaging

- Eligibility criteria: ensure subject continues to meet study eligibility (if longer than 60 days since screening)
- Medical history: capture additional medical history since screening (if longer than 60 days since screening)
- Concomitant medications: record medications taken since screening through day of surgery (if longer than 60 days since screening)
- There will be a  $\geq 4$  week wait period between prior biopsy and protocol related MR imaging to allow for resolution of hematomas.
- $^{68}\text{Ga}$ -PSMA-11 PET-CT and mpMRI:

- Patient receives a ~3-5 mCi dose of Ga-PSMA-11. (A physician-sponsored IND has been successfully obtained)
- Patient will undergo research Vision PET-CT and SOC MRI at Goodman Hall (or similar facility) which is anticipated to last approximately 60 minutes. Per our institutional standard of care, patients will receive intravenous iodinated contrast with the PET-CT unless medically contraindicated.
- Imaging Protocol for Ga-PSMA-11 PET Data Acquisition (approximate times):

Time (minutes)	Activity
- 60	Patient arrives, and completes consent forms, while radiopharmaceutical synthesis and quality control procedures are completed.
0	Administer  Ga-PSMA-11, 3-5 mCi (outside the camera).
5-50	Start standard-of-care pelvic MR acquisition with simultaneous collection of  Ga-PSMA-11 PET.
50-55	Patient can leave camera and depart.

- The PET read will be done by a board certified nuclear medicine specialist (e.g. [name] or similar) and the MRI read will be done by a board certified MR radiologist (e.g. [name] or similar). Suspicious lesions will be marked in a blinded fashion.
- AE assessment: AEs will be assessed at the time of Ga-PSMA-11 administration and also at the appointment for biopsy (if done) any event not expected is collected including but not limited to: rash and shortness of breath.
- Safety monitoring following radiopharmaceutical administration will consist of visual and verbal monitoring of the patient after injection, and during and at the conclusion of the PET/CT procedure, with any apparent patient abnormalities, reactions or reported effects noted in the study records.
- The nuclear medicine technologists administering the radiopharmaceutical are responsible for immediately reporting any adverse or unexpected events to the principal investigator or clinical

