### **7.3.3 PET, MRI Biopsy:**

- Patients proceeding to surgery following PSMA PET and MRI may forgo biopsy.
- Patients not proceeding to surgery will undergo a SOC MRI-fusion biopsy based on the pre-biopsy scan detailed in 7.3.2. PET findings will be integrated into the planning of the fusion biopsy. See appendix C for details of the fusion biopsy.
- AE assessment: AEs will be assessed at the time of Ga-PSMA-11 administration and also at the appointment for biopsy (if done) any event not expected is collected including but not limited to: rash and shortness of breath.
- A sextant-based analysis will be performed. See appendix D for details of sextant analysis.
- A secondary “per lesion” analysis will also be performed.

- How the knowledge of the PSMA-PET informs treatment will be tracked. Examples of informing the decision include PSMA-PET detected additional intraprostatic cancer lesions diagnosed.

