## **8 STUDY WITHDRAWAL/DISCONTINUATION**

Subjects must be discontinued from the study for the following reasons:

- Withdrawal of consent
- Investigator deems withdrawal necessary at any time if it is determined that it is not in the subjects best interest to continue, or if the subject is found to be noncompliant with study procedures.

If subject discontinues after administration of study drug, he or she will be encouraged to continue on study for safety procedures per protocol. Reason(s) for discontinuing must be clearly documented in the appropriate source documents.

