## 12.2 Adverse Event Reporting Requirements:

Adverse events will be recorded for the first study drug administration and also for the prostate biopsy (if indicated) regardless of whether or not the event(s) are considered related to trial medications. All AEs considered related to trial medication will be followed until resolution, return to baseline, or deemed clinically insignificant, even if this occurs post-trial.

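### Any death within 28 days of the last dose is an SAE, but surgical men who forgo biopsy have no scheduled AE/SAE check after the PET/CT, and biopsied men are not guaranteed one at or after day 28

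*Combined protocol and SAP*

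**What the plan says.** Section 12.1.2 counts as serious an event that "Results in death or ANY death occurring within 28 days of last dose of study drug", whether or not the tracer is thought responsible. The 28 days attach to death only; the other SAE criteria carry no time limit.

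Collection is described in three places. Section 7.3.2 has AEs assessed at tracer administration and "also at the appointment for biopsy (if done) any event not expected is collected"; section 7.3.3 repeats this. Section 12.2 reads "Adverse events will be recorded for the first study drug administration and also for the prostate biopsy (if indicated" (the bracket closes there), with attribution not affecting whether an event is recorded. On the scan day, section 7.3.2 provides for "visual and verbal monitoring of the patient after injection, and during and at the conclusion of the PET/CT procedure", and its timetable lets the patient go at about 50-55 minutes after injection.

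On the patient's path, section 7.3.3 states: "Patients proceeding to surgery following PSMA PET and MRI may forgo biopsy". The synopsis has patients "followed until biopsy and/or surgical resection", with no number of days after the dose. Section 7.3.4 (Surgery and Pathology) contains no AE item, and the study calendar in 7.2 has no AE row. The calendar's second footnote and section 7.3.2 both allow a second tracer injection about 6-12 months after the first.

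**The concern.** A definition with a 28-day reach needs some way of learning what happened in those 28 days. Here the scheduled observation stops at the end of the scan for one group of men. For the other group it stops at a biopsy visit whose date is not tied to the dose. A site could follow every scheduled step and still not know whether its own SAE rule had been met.

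What is at stake is the completeness of the safety record. Section 11 requires the DSMC chair to be told at once if grade 3 or higher events become more frequent than the reference document reports. That comparison is only as good as the ascertainment behind it. The imaging endpoints are not affected.

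**Working it through.** The plan gives no figure to reproduce, so the check sets the SAE rule against each place where an event could be picked up.

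**Surgical man, no biopsy**
- Administration and scan (7.3.2): observed from minute 0 to about minute 55.
- Biopsy appointment (7.3.3): does not occur.
- Surgery (7.3.4): no AE item, whether surgery falls before or after day 28.
- Study calendar (7.2): no AE row and no later contact.
- Scheduled monitoring as a share of the window: 28 × 24 × 60 = 40,320 minutes; 55 / 40,320 = 0.14%. This describes the schedule, not the chance of missing an event.

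**Man who has a biopsy**
- Observed at the scan and again at the biopsy on day *t* after injection.
- If *t* ≥ 28, that visit can cover the whole window in retrospect. If *t* < 28, then 28 − *t* days have no later scheduled check. Taking *t* = 14 as an assumed example, 14 days are left.
- The documents do not fix *t*. Section 7.3.2 also says that men who do not have a prostatectomy have no further study procedures.

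**Second injection**
- 12.1.2 counts from the *last* dose; 12.2 records for the *first* administration. With a second injection 6-12 months later, the 28-day window follows an injection that 12.2 does not name. The assessment item in 7.3.2 is not limited to the first injection, so it does not agree with 12.2 either.

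**Do other sections close the gap?**
- Section 11 (continuous review, weekly meetings, semi-annual DSMC review) works on events already recorded.
- Section 11.4 sets a one-business-day limit for entering an SAE, but the clock starts when the team is told.
- Section 12.2 follows AEs to resolution only if they are known and judged related; the death rule includes unrelated deaths.
- Section 8 says of a man who discontinues after dosing that "he or she will be encouraged to continue on study for safety procedures per protocol". For a surgical man without biopsy, none is scheduled after the scan.

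None of these schedules a contact to find an event.

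**Number of men affected:** the schema in section 2 leaves the split between prostatectomy and surveillance open, and 7.3.3 makes forgoing biopsy optional. The number without any post-scan check could therefore be anything from 0 to 36.

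**The case against.** The best counter-argument is that 12.1.2 classifies deaths and does not set a visit schedule. A definition may properly be wider than the visits, since it also governs events that arrive by other routes. Those routes exist: enrolment is at one institution, patients come mostly through its urology clinic, prostatectomy specimens are read there under routine care, and the team meets weekly on safety. Section 7.3.2 describes sub-pharmacologic dosing, more than 100 patients imaged locally, and adverse events as very improbable. Light AE collection can be defended as proportionate.

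Much of this stands. A reader might infer that surgical men go unobserved for 28 days, or that a site would hear of a death or hospitalisation only by luck. The documents do not support that: spontaneous notification and routine surgical care could bring such events to the team. Nor do they support treating 28 days as a collection window for every kind of event, because the limit is attached to death alone.

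What does not stand is the idea that oversight fills the gap. The review and reporting sections act on known events. Expecting few events is not a way of checking whether any occurred, and the study is run under the institution's monitoring plan for high-risk trials.

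**Conclusion.** The point holds as a gap in scheduled ascertainment. Surgical men who forgo biopsy have no scheduled AE/SAE check after the PET/CT. Biopsied men have one, but nothing places it at or after day 28. Sections 12.1.2 and 12.2 also disagree on which injection counts. These conclusions rest on the text alone; the only assumption is that no AE contact is hidden in a figure that is not shown.

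The size is modest. The number of men affected is not determined by the documents, and no sensitivity, specificity or ROC result depends on the point. A reader might go further and compute an upper confidence limit for the SAE rate from the men who were checked. That is not warranted: the plan has no safety objective or endpoint, proposes no such rate, and fixes no split from which to take a denominator. This is a cheap improvement, not a flaw that threatens the trial's conclusions.

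**What to change.** - In 7.3.2, 7.3.4, 12.2 and the study calendar, add one AE/SAE and vital-status check for every man, covering the 28 days after each tracer injection. A chart review or phone call at or after day 28 is enough. The 7.3.2 line that ends study procedures for men without prostatectomy needs a matching exception.
- Change the reference to the *first* administration in 12.2 so that it agrees with the *last* dose in 12.1.2 when a second injection is given.
- In the synopsis, state that safety follow-up runs to the later of day 28 and biopsy or surgery.

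The cost is protocol wording plus 36 × 1 = 36 checks, rising to at most 36 × 2 = 72 if every man has the second scan. No extra visit or procedure is needed. The drawback is that some unrelated peri-operative events will be found and must be attributed; section 12.1.4 already supplies the categories.
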